**Evaluation of cognitive state in senior subjects using
Neurosteer single-channel EEG with an interactive assessment tool**

Clinical Research Center

Neurosteer Ltd.

Protocol

Version 3.0

05:2021

May 2021

Protocol Summary

OBJECTIVE	To evaluate the ability to differentiate between cognitive states in the senior population using a single-channel EEG with an interactive assessment tool.
STUDY DESIGN	This is an observational study. Patients who fulfill all inclusion criteria and none of the exclusion criteria will be enrolled in the study, be neurologically evaluated and will go through EEG recordings while listening to an auditory cognitive assessment tool and performing tasks. EEG recordings will be analyzed using proprietary computational analyses.
STUDY POPULATION	The study population is comprised of senior patients.
SAMPLE SIZE CONSIDERATIONS	80 subjects
INCLUSION CRITERIA	
 1. Men and women over the age of 50. 2. MMSE \geq 24 3. Patient is able to collaborate. 4. No other cognitive comorbidities. 5. No seizure events.
EXCLUSION CRITERIA	
 1. MMSE $<$ 24 2. Any verbal or non-verbal form of objection from patient or from patient's family member or significant other. 3. Presence of several cognitive comorbidities. 4. Damage to integrity of scalp and/or skull. 5. Skin irritation in the facial and forehead area. 6. Significant hearing impairments. 7. History of drug abuse.
STUDY PROCEDURES	
Clinical staff will identify potential subjects and will examine the eligibility of subjects according to inclusion and exclusion criteria.
 
Research staff will inform the patient on study's objective and design. Patients will sign the Informed Consent Form (ICF). Patients will be divided into groups according to their initial MMSE score (mild cognitive impairment MMSE 24-27 and healthy seniors MMSE 28-30). Research staff will set up an initial assessment session using the Neurosteer system. In this session the patient will listen to the auditory assessment battery and perform tasks. The patient will be re-examined in the same experimental setting over the next 7 days and at least 1 day later. Level of cognition will be assessed by Neurosteer technology.

DATA TO CAPTURE	
The following data will be collected for the purposes of this study:
 
Demographics: age, gender.
 
Clinical data: official diagnosis, MMSE score, IADL score, comorbidities, drugs.
 
Medical history: number of years with the disease.
 
Measurements of the research: electrophysiological data captured by Neurosteer system.

TECHNICAL DESCRIPTION OF THE SYSTEM	
The system is composed of hardware and software modules that facilitate the capture and interpretation of electrophysiological data as well as enable viewing the processed data in real time and offline. An electrode patch is attached on the subject's forehead to capture the electrophysiological signal. The signal is sent via low energy Bluetooth to an EEG Monitor. The signal is then sent via Wi-Fi to the cloud where the data is stored on a HIPAA compliant server. Data analysis performed in the cloud transforms the electrophysiological signal into easily readable data of brain activity, which is accessible via any web interface. The brain activity features (BAFs), which comprise the main novelty of the method, are created using a variant of the wavelet packet analysis and the best basis algorithm. Statistical analysis will be performed on the data.

STATISTICAL ANALYSIS PLAN	
MMSE scores will be taken from previous evaluation performed in the institute. Each patient will be evaluated twice, using the continuous measurement by the Neurosteer system. Statistical analyses will include Pearson correlations between electrophysiological data and MMSE scores, and reaction times in the tasks. Linear mixed models (LMM) will be calculated with group and task level as independent variables.

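### The objective is to differentiate cognitive states, but the planned correlations and mixed model do not measure how well the EEG separates the two MMSE groups

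*Combined protocol and SAP*

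**What the plan says.** The Objective row gives the aim as "To evaluate the ability to differentiate between cognitive states in the senior population", using a single-channel EEG with an interactive assessment tool. Under Study Procedures, "Patients will be divided into groups according to their initial MMSE score": 24-27 is labelled mild cognitive impairment and 28-30 healthy. The same row adds that "Level of cognition will be assessed by Neurosteer technology".

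The Statistical Analysis Plan row names two analyses: "Statistical analyses will include Pearson correlations between electrophysiological data and MMSE scores, and reaction times in the tasks", and "Linear mixed models (LMM) will be calculated with group and task level as independent variables". It also says that "MMSE scores will be taken from previous evaluation performed in the institute", and that each patient is evaluated twice.

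The documents name no ROC area, sensitivity, specificity, accuracy, cut-off or classification rule. They designate no brain activity feature as the outcome and do not name the mixed model's dependent variable. Study Design says only that "EEG recordings will be analyzed using proprietary computational analyses".

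**The concern.** A mixed model with group as a predictor asks whether the mean EEG measure differs between the MMSE groups. A Pearson correlation asks whether the measure moves with the score. The objective asks whether the EEG can tell the states apart, which depends on how far the two distributions overlap. A mean difference can be clearly non-zero while most of the two distributions coincide.

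The plan does not commit to reporting effect sizes or intervals. Followed as written, it would allow a significant group effect or correlation to be reported as ability to differentiate, even though a patient's EEG value said little about which group the patient belongs to.

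**Working it through.** **The plan's own figure.** The only number is 80 subjects, under Sample Size Considerations. It comes without alpha, power, effect size, SD or group split, so it can be neither reproduced nor refuted. This point does not depend on it being right or wrong.

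**Inputs.** From the documents: N = 80; groups MMSE 24-27 and 28-30. Assumed, for illustration only: two-sided alpha 0.05; one normally distributed feature with equal variance in both groups; one value per patient; a split of 40/40, or of 20 (MMSE 24-27) and 60 (MMSE 28-30).

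**Step 1: smallest significant group difference.** In units of the SD of the per-patient value, d = t(0.975, 78) × √(1/n1 + 1/n2), with t = 1.991.

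- 40/40: 1.991 × √(1/40 + 1/40) = 1.991 × 0.2236 = 0.445
- 20/60: 1.991 × √(1/20 + 1/60) = 1.991 × 0.2582 = 0.514

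**Step 2: the separation this implies.** Under the equal-variance normal model, area = Φ(d/√2), sensitivity = specificity = Φ(d/2) at the midpoint cut-off, and overlap = 2Φ(−d/2).

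| Split | d | ROC area | Sens = spec | Overlap |
|---|---|---|---|---|
| 40/40 | 0.445 | 0.624 | 58.8% | 82.4% |
| 20/60 | 0.514 | 0.642 | 60.1% | 79.7% |

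**Step 3: the same for the correlation.** Smallest significant r = t/√(t² + 78) = 1.991/√(3.96 + 78) = 0.220, so r² = 0.048, about 5% of variance.

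**Step 4: is this only a boundary case?** Take a true area of 0.67. Then d = √2 × Φ⁻¹(0.67) = 0.622, sensitivity = specificity = Φ(0.311) = 62%, and overlap = 2Φ(−0.311) = 76%. The noncentrality is 0.622/0.2236 = 2.78 (40/40) or 0.622/0.2582 = 2.41 (20/60). Power from the noncentral t is 0.785 or 0.663; a simulation of 20,000 runs gave 0.779 and 0.665. A significant test alongside weak separation would be the likely result at that area.

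**Step 5: precision if the area is reported.** Hanley-McNeil standard error at area A = 0.75, with Q1 = A/(2 − A) = 0.600 and Q2 = 2A²/(1 + A) = 0.643:

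SE = √{[A(1 − A) + (n1 − 1)(Q1 − A²) + (n2 − 1)(Q2 − A²)]/(n1·n2)}

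- 40/40: √(4.784/1600) = 0.0547; half-width 1.96 × 0.0547 = 0.107
- 20/60: √(5.641/1200) = 0.0686; half-width 1.96 × 0.0686 = 0.134

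**The case against.** The best reply is that differentiation can be read at group level. The study is observational, claims no diagnostic use and sets no cut-off, and a mixed model with a group factor is an ordinary way to ask whether a signal differs between groups. This stands in part. A reader might infer that the plan leaves its objective unanalysed, and the documents do not support that: both named analyses bear on it. What is missing is the measure of separation.

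Second, under the equal-variance normal model the area is a function of the standardised difference, so reporting that difference with its CI would convey the same information. This is right as far as it goes. But the plan does not commit to reporting it, and an empirical ROC area does not need the normal model.

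Third, the wording of the analysis sentence and the reference to proprietary analyses leave room for a discrimination analysis. They do, but they specify none.

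Fourth, a reader might take this point as evidence that an EEG feature will be picked after the data are seen. The documents do not show that. The lack of a designated feature is a separate gap: it affects the correlations and the mixed model equally, and an ROC area alone would not cure it.

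Finally, a two-group area discards gradation within each group. That is true, and it is a reason to keep the correlation with the MMSE score.

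**Conclusion.** The point holds as a mismatch between the objective and the named analyses, and it should be fixed. The planned analyses are valid for group-level questions but do not quantify how well the EEG separates MMSE 24-27 from MMSE 28-30. That conclusion needs no arithmetic.

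The size does rest on assumptions outside the documents (those listed under the inputs). Under them, a just-significant result with 80 patients corresponds to an area of 0.62 to 0.64 and about 80% overlap. This describes what a significance test can and cannot show at this sample size. A reader might infer that the device separates the groups poorly; the documents contain no results and support no such prediction.

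Nor do the documents support a demand for threshold accuracy, a second reference standard or a success margin. The plan sets out no classification rule and no confirmatory claim.

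**What to change.** Before the data are examined:

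1. Name one EEG score and one value per patient, for example the mean of both sessions.
2. Report its ROC area with 95% CI for MMSE 24-27 versus 28-30. Describe it as agreement with the MMSE grouping, not as diagnostic accuracy, since the groups are defined by a previously recorded MMSE score.
3. If the score is built or selected on these data, estimate the area by patient-level cross-validation, with both sessions of a patient in the same fold and the building or selection repeated inside each fold.
4. Keep the mixed model and correlations, and report the group difference and r with 95% CI.

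Optional, and needed only if a classification or confirmatory claim is intended: sensitivity and specificity at a threshold; a repeat against the official diagnosis, which is already collected ("Clinical data: official diagnosis, MMSE score, IADL score, comorbidities, drugs"); and a minimum area for the lower confidence limit.

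The cost is small. No new patients, visits or measurements are needed, but the sponsor must commit to one score where the documents name none. Precision will be modest, as step 5 shows, and the result may look less favourable than a p-value.

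### Age and gender are collected but enter neither planned analysis, so an age difference between the MMSE groups could pass for a cognitive effect

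*Combined protocol and SAP*

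**What the plan says.** The Study Design row of the Protocol Summary states "This is an observational study", and the Objective row gives the aim: "To evaluate the ability to differentiate between cognitive states in the senior population using a single-channel EEG with an interactive assessment tool". Under Study Procedures, "Patients will be divided into groups according to their initial MMSE score", with 24-27 labelled mild cognitive impairment and 28-30 labelled healthy. The only age rule under Inclusion Criteria is "Men and women over the age of 50", with no stated upper limit. Data to Capture lists "Demographics: age, gender".

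The Statistical Analysis Plan names two analyses. The first is correlation: "Statistical analyses will include Pearson correlations between electrophysiological data and MMSE scores, and reaction times in the tasks". The second is the mixed model: "Linear mixed models (LMM) will be calculated with group and task level as independent variables". No covariate, partial correlation, matching, stratification or sensitivity analysis for age or gender is stated anywhere in the document.

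**The concern.** The comparison is not randomised, so nothing in the design makes the two MMSE groups alike in age or gender. The group coefficient and the EEG-MMSE correlation are the quantities that bear most directly on the objective. Run as written, each of them absorbs any influence of age that is shared by the EEG feature and the MMSE score. The correlations involving reaction time are open to the same problem if age relates to both variables in the pair. A reader could then take an age effect for evidence that the device distinguishes cognitive states.

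Because age is recorded, an adjusted analysis can still be run later. Without a rule set beforehand, though, the choice between adjusted and unadjusted results would be made after the data are seen.

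**Working it through.** **Inputs from the document.** 80 subjects (Sample Size Considerations); two groups defined by MMSE; the mixed-model terms and the Pearson correlations as stated. The document gives no age distribution, no age-MMSE or age-EEG relation, no group sizes and no significance level. It therefore contains no figure on this point to reproduce, and what follows is illustration.

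**Assumptions (not in the document).** Age, MMSE and EEG jointly normal; one EEG summary per subject; no EEG-MMSE link once age is held fixed; lowest 40 of 80 MMSE values as the low group; two-sided 0.05. Correlations are given by size; their signs affect only the direction of the bias.

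**Step 1, Pearson test.** With no link given age, the spurious correlation is

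r = corr(age, MMSE) × corr(age, EEG).

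By Fisher's z with standard error 1/√77, the shift is δ = atanh(r) × √77 and the rejection rate is Φ(δ − 1.96) + Φ(−δ − 1.96). For correlations of 0.3 and 0.3: r = 0.09, δ = 0.0902 × 8.775 = 0.792, and the rate is 0.121 + 0.003 = 0.124.

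**Step 2, group test in the same scenario.** For a median split of a normal variable, the mean age gap is about 2√(2/π) × corr(age, MMSE) = 1.596 × corr(age, MMSE). That gives 0.32, 0.48 and 0.64 SD for correlations of 0.2, 0.3 and 0.4; simulation with 80 subjects gives 0.63 for the last. Multiplying by corr(age, EEG) gives the spurious EEG difference: 0.32 × 0.2 = 0.06 SD, 0.48 × 0.3 = 0.14 SD, 0.63 × 0.5 = 0.315 SD. Rejection rates are simulated with 40,000 data sets per row; where a range is shown, repeat simulations differed in the rounding.

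| age-MMSE | age-EEG | spurious r | Pearson rejects | group test rejects |
|---|---|---|---|---|
| 0 | 0.5 | 0 | 5.0% | 5% |
| 0.2 | 0.2 | 0.04 | 6.4% | 6% |
| 0.3 | 0.3 | 0.09 | 12.4% | 10% |
| 0.4 | 0.3 | 0.12 | 18.5% | 13-14% |
| 0.3 | 0.5 | 0.15 | 26.4% | 18-19% |
| 0.4 | 0.5 | 0.20 | 42.8% | 29% |

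With a 20/60 split the group test rejects about 9% of the time at (0.3, 0.3) and 25% at (0.4, 0.5).

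**Step 3, scale.** A 40/40 comparison has 80% power for a difference of (1.960 + 0.842) × √(1/40 + 1/40) = 0.63 SD. The spurious 0.315 SD in the last row is half of that.

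**Step 4, adjustment.** With age and gender in the model, both tests reject 4.8% to 5.3% of the time in every case run. This is expected, since the simulated age effect is linear and the adjustment has the same form.

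**The case against.** The harm needs two conditions, a link between age and MMSE group and a link between age and EEG, and the document establishes neither. If either is absent there is no bias, and at correlations of 0.2 the inflation is negligible. Eligibility confines MMSE to 24-30, which tends to weaken its correlation with age. The larger rows must therefore be read as correlations within that narrow range, and they may be on the high side. This stands, and it is why the figures are illustrative.

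The return to about 5% after adjustment follows from how the scenario is built. In real data, linear adjustment works only if the age relation is roughly linear and the groups overlap in age. The bias shown applies to the group main effect and the correlations, not to a within-subject task-level contrast, unless age changes the response to task level. If a group-by-task-level interaction is intended (the plan does not say), an age main effect alone would not protect it. The effect of gender is not quantified. These limits also stand.

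Two further arguments carry less weight. The plan says its analyses will include those listed, so adjustment is not ruled out; but the model terms are named and age is not among them. Unadjusted discrimination is also a legitimate question, which is a reason to report both results rather than to leave the choice open.

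**Conclusion.** The concern holds. It is certain that age and gender are collected and that neither enters a stated analysis, in an observational comparison with nothing to balance them. The consequence is conditional: no inflation if age is unrelated to MMSE or to EEG, about 6% at weak correlations, and 12% to 43% (Pearson) or 10% to 29% (group test) at moderate ones. Those figures rest on the assumed correlations, normality, a 40/40 split and one EEG value per subject. The point should be fixed, but it does not invalidate the study, because the data needed for adjustment will exist. Confidence in the size is only moderate.

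**What to change.** In the Statistical Analysis Plan:

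- List the mixed-model fixed effects as group, task level, age (continuous) and gender. If a group-by-task-level interaction will be tested, add age-by-task-level as well.
- For the EEG-MMSE and reaction-time associations, report partial correlations, or linear regression, adjusted for age and gender.
- Report the unadjusted results alongside, and state in advance which set supports the main conclusion.
- Tabulate age and gender by group, so that overlap can be judged, and check that the age relation is roughly linear.
- Adjustment for drugs is optional, as a sensitivity analysis with the drug classes named beforehand.

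The cost is wording, plus two degrees of freedom out of 80 subjects for age and gender main effects; the adjusted effect may be smaller. Power can move either way. For a true group difference of 0.65 SD with a 40/40 split, it falls from about 83% to 77% if age correlates 0.4 with MMSE but not with EEG. It rises from about 82% to 91% if age correlates 0.5 with EEG but not with MMSE.

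### Medication is collected and not restricted, but no planned analysis uses it, so any imbalance in centrally acting drugs between MMSE groups would pass into the cognitive-state contrast

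*Combined protocol and SAP*

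**What the plan says.** All the relevant text is in the Protocol Summary.

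- **Study design:** "This is an observational study". Under Study Procedures, the groups are formed from the initial MMSE score: "mild cognitive impairment MMSE 24-27 and healthy seniors MMSE 28-30".
- **Eligibility:** the only drug-related criterion is the exclusion "History of drug abuse". Criteria such as "No other cognitive comorbidities" and the one on seizures restrict diagnoses and events, not prescriptions.
- **Data to capture:** the clinical data are "official diagnosis, MMSE score, IADL score, comorbidities, drugs". How often medication is recorded is not stated.
- **Statistical analysis plan:** "Linear mixed models (LMM) will be calculated with group and task level as independent variables". It also names Pearson correlations involving the electrophysiological data, MMSE scores and reaction times. No covariate, partial correlation, stratification or sensitivity analysis is named.

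**The concern.** The objective is to tell cognitive states apart from a single EEG channel. Centrally acting drugs can alter the EEG. Because the groups are observed and not randomised, nothing in the design balances their use. If patients with MMSE 24-27 take more of them than patients with MMSE 28-30, the group term in the LMM contains both any cognitive-state difference and the drug difference. The EEG-MMSE correlation is exposed in the same way.

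The second recording does not help. Usual medication and group are both fixed within a patient over the 1 to 7 days between sessions, so neither the repeat session nor a patient-level random effect separates them. Adjusting for age and gender would not help either, since two patients alike on both can differ in medication.

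The study's main conclusion would then be open to an obvious alternative explanation, although the field needed to examine it is already being collected.

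**Working it through.** **Inputs from the documents.** 80 subjects in total; groups MMSE 24-27 and 28-30; LMM terms group and task level. Group sizes, significance level, variance and medication prevalence are not given, so there is no figure of the plan's own to reproduce on this point.

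**Assumed inputs.** 40 per group, one EEG feature with residual SD 1, one value per patient, no true cognitive effect, two-sided 0.05. Let p1 and p0 be the shares of users in the lower- and higher-MMSE groups, and d the drug effect in SD units.

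**Formulas.**

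- Spurious group difference: b = (p1 − p0) × d
- Standard error: SE = √{[1 + p1(1 − p1)d²]/40 + [1 + p0(1 − p0)d²]/40}
- False-positive rate: two-sided rejection probability of the noncentral t with 78 degrees of freedom and noncentrality b/SE

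**Results.**

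| p1 | p0 | d | b (SD) | SE | b/SE | False-positive rate |
|---|---|---|---|---|---|---|
| 0.30 | 0.20 | 0.5 | 0.05 | √(1.0525/40 + 1.04/40) = 0.229 | 0.22 | 5.5% |
| 0.40 | 0.20 | 0.8 | 0.16 | √(1.1536/40 + 1.1024/40) = 0.237 | 0.67 | 10.2% |
| 0.50 | 0.20 | 1.0 | 0.30 | √(1.25/40 + 1.16/40) = 0.245 | 1.22 | 22.7% |

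With p1 = p0, b = 0 and the rate stays at 5%.

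**Does a medication term remove it?** Simulation with 40 per group and 5,000 runs per case. MMSE scores were drawn uniformly within each group's range for the Pearson test:

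| Use, lower vs higher MMSE | d | Group test, no drug term | Group test, with drug term | Pearson with MMSE, unadjusted |
|---|---|---|---|---|
| 30% vs 30% | 0.5 | 4.7% | 4.5% | 4.5% |
| 40% vs 20% | 0.5 | 7.2% | 5.1% | 6.6% |
| 50% vs 20% | 0.8 | 16.9% | 5.3% | 14.3% |

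The term restores about 5% when it is correctly specified.

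**Is one yes/no flag enough?** Not necessarily. Suppose class A (0.8 SD) is used by 30% vs 10%, class B (no effect) by 10% vs 10%, with no overlap.

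- Unadjusted bias: 0.20 × 0.8 = 0.16 SD.
- The pooled flag is present in 40% vs 20%, with mean effect among flagged patients of 0.6 vs 0.4 SD.
- Its fitted coefficient is (0.24 × 0.6 + 0.16 × 0.4)/(0.24 + 0.16) = 0.52.
- Remaining bias: 0.16 − 0.20 × 0.52 ≈ 0.06 SD.

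Coding by class therefore matters.

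**The case against.** Five points can be made on the other side.

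1. **Enrolment and imbalance are not documented.** A reader might infer that medicated patients are known to be enrolled and that the groups differ in their use. The text only lacks a criterion against such patients and gives no figures. This stands: the bias is conditional on an imbalance.
2. **The analysis list is open-ended.** A reader might conclude that the study cannot separate drug effects from cognitive state. That goes too far. The plan says what the analyses will include, and the drug data will be there, so an adjusted analysis remains possible. What is missing is pre-specification; an adjustment chosen after seeing the results carries less weight.
3. **The size rests on assumptions.** The mildest case is negligible, and the largest needs a 30-point gap and a full-SD effect. Drug classes may also act in different directions, so the net bias could be smaller or of either sign. This stands.
4. **Adjustment changes the question.** The aim is discrimination, and a patient whose cognition is lowered by a drug still belongs to the lower-MMSE group. Some drugs are also prescribed because of impairment, so adjusting for them can remove real signal. This stands, and it is why the adjusted model should sit beside the planned one and not replace it.
5. **Medication is one part of a wider gap.** Age, gender and comorbidities are also collected and not named in the model. True, but settling those covariates would not settle medication.

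A reader might also infer that drugs are recorded only once, so that a drug taken before one session would be missed. The documents give no recording frequency and do not support that. The effect on reaction time is likewise less certain, because the LMM outcome is not named and the correlation sentence is ambiguous.

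**Conclusion.** The gap is real: medication is unrestricted, collected and unused in the stated analyses of a non-randomised comparison. If centrally acting drug use differs by MMSE group and affects the EEG, the effect goes straight into the group contrast and the EEG-MMSE correlation. Its size cannot be derived from the documents; the 5.5% to 23% range holds only for the assumed inputs, and the bias is zero if use is equal. The documents do not support saying that the groups do differ in medication, or that the planned analysis is invalid. They do support pre-specifying a check, which the sponsor should do.

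**What to change.** Amend the statistical analysis plan as follows.

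- **Code and tabulate.** Before EEG data are linked to MMSE, code the collected drug field by class: centrally acting drugs not prescribed for cognition, separated by class where numbers allow, and anti-dementia drugs. Tabulate use by MMSE group.
- **Keep the planned LMM and correlations**, and pre-specify beside them: (1) the LMM with centrally acting drug use as a fixed effect, with the matching partial correlations; and (2) the group contrast without patients on anti-dementia drugs.
- **Report** planned and adjusted estimates side by side with confidence intervals. If the adjusted estimate is materially attenuated, state that the group difference cannot be attributed to cognitive state alone. Write down in advance what counts as material.

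**Cost.** Plan wording and the coding of a field already collected; no change to eligibility, sample size, study visits or anyone's treatment. The downsides are a few degrees of freedom, possible over-adjustment where a drug was prescribed because of impairment (hence both results are shown), and fewer patients in the restricted analysis.
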